The effect of the intervention on the secondary outcomes will be characterized by the change in each measure during each of the study phases. Repeated measures analysis of variance models (RM-ANOVA) will be fit to the measurements to evaluate the change over time from baseline (Visit 3 – to allow for stabilization of control on 4 weeks of low dose inhaled corticosteroid) to the end of the inhaled corticosteroid-stable phase, as well as the change over time during the inhaled corticosteroid-taper phase. These changes over time will be estimated and compared between the treatment groups with the specification of appropriate contrast statements, and a modified auto-regressive correlation structure will be specified to reflect the longitudinal design. Repeated measures analysis of

covariance models (RM-ANCOVA) will also be fit to the secondary outcomes as discussed above, with potential adjustment for the baseline covariates listed above. The secondary outcome measuring time to exacerbation will be evaluated using survival analysis methods as described for the primary outcome.

The secondary hypothesis to evaluate the effect of the intervention within overweight participants and African Americans will be addressed by fitting RM-ANOVA models to the lung function measures within those participants with BMI ≥ 25 and within African Americans. As described above, the models will compare the change in lung function measurements over the treatment period between the intervention groups. A RM-ANCOVA model will also be fit within each of these subgroups to compare the change in lung function measures between the intervention and control groups with adjustment for the appropriate baseline factors included above. Assuming we will have approximately 50% of randomized participants in the overweight category, and approximately 30-40% African Americans, we will have the following power to detect the following effect sizes to address this secondary hypothesis.

Power estimates assuming an overall alpha=0.05, 2-sided tests, 15% withdrawal, and using change in $FEV_1(L)$ as the lung function measure with standard deviation = 0.375 from the ACRN MIA trial

Subset	Sample size	Power	Effect Size
Overweight/obese	100 per group (50%)	80%	0.16 L
· ·		85%	0.17 L
		90%	0.19 L
African American	80 per group (40%)	80%	0.18 L
		85%	0.19 L
		90%	0.21 L
		80%	0.21 L
	60 per group (30%)	85%	0.23 L
		90%	0.24 L

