Additional exploratory analyses will be performed for this secondary hypothesis which include estimating the treatment effect within those who are **not** overweight/obese, and among those who are **not** African-American, and evaluating the corresponding tests of interaction within the RM-ANOVA

framework.

1

2

3

4

5

6

7

8

9

10

11

12

13

14

15

16

17

18

19

20

21

22

23

24

25

The secondary hypothesis to evaluate the effect of the intervention among those participants who have reduced corticosteroid responsiveness will be addressed by fitting RM-ANOVA models to the lung function measures within those who meet criteria for reduced corticosteroid responsiveness defined by lung function change after oral corticosteroid. Corticosteroid-responsive airflow obstruction will be defined as a ≥5% improvement in FEV₁ after the administration of 5 + 2 days of prednisone 40 mg/day measured at visit 4 compared to the baseline value at visit 3. If the participant's FEV₁ does not improve by 5%, they will be considered to have corticosteroid-nonresponsive airflow obstruction. Because there may not be consensus on the best criteria to use to define corticosteroid responsiveness, we will perform additional exploratory analyses considering the following alternative cutoffs: median split, 7.5% change in FEV₁, 10.0% change in FEV₁, as well as defining those with FEV₁ >85% of predicted after the corticosteroid burst as responders. RM-ANCOVA models which adjust for relevant covariates will also be evaluated. If we expect to find approximately 40-50% of randomized participants with reduced corticosteroid responsiveness, we will have 80-90% power to detect a difference in the change in FEV₁ between the two treatment groups in the range of 0.16 L to 0.21 L as shown in the table above. An additional exploratory analysis will be performed for this secondary hypothesis which includes estimating the treatment effect within those who are corticosteroid responsive, and evaluating the corresponding test of interaction within the RM-ANOVA framework. A second exploratory analysis for this hypothesis will involve treating corticosteroid responsiveness as a continuous measure, and assessing its association with change in lung function in the repeated measures models.

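### Conditioning on the Visit 3 value, rather than only subtracting it, would sharpen the lead tests of the continuous secondary outcomes at almost no cost

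*Protocol*

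**What the plan says.** Protocol section VIII.B describes the secondary outcomes by their change. An RM-ANOVA is fitted to the repeated measurements, with two changes of interest: from Visit 3 to the end of the ICS-stable phase, and across the taper phase. It continues: "These changes over time will be estimated and compared between the treatment groups with the specification of appropriate contrast statements". Visit 3 is before randomisation, which takes place at Visit 4 (sections V.C and VI.C).

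The two lung-function hypotheses use the same approach. For overweight participants and African Americans, "the models will compare the change in lung function measurements over the treatment period between the intervention groups". For corticosteroid non-responders, the hypothesis is addressed by "fitting RM-ANOVA models to the lung function measures within those who meet criteria for reduced corticosteroid responsiveness".

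Covariate adjustment comes in a further RM-ANCOVA, in general "with potential adjustment for the baseline covariates listed above". The list referred to stands with the secondary adjusted Cox model in the same section. It contains FEV1 % predicted and log2 PC20. It does not contain the baseline value of the Asthma Control Test (ACT), the Asthma Symptom Utility Index (ASUI), asthma-control or rescue-free days, the Asthma Bother Profile (ABP) or the Sinonasal Questionnaire (SNQ).

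The subgroup power table is headed "Power estimates assuming an overall alpha=0.05, 2-sided tests, 15% withdrawal" and uses change in FEV1 in litres "as the lung function measure with standard deviation = 0.375 from the ACRN MIA trial".

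**The concern.** Because Visit 3 comes before randomisation, any difference between the arms there is chance. A contrast of changes subtracts that difference in full, although on average only a fraction rho of it carries forward to later visits. The over-correction adds noise. Using the Visit 3 value as a covariate, or giving both arms one Visit 3 mean, removes only the part that carries forward and so gives a smaller standard error from the same data.

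What is at stake is precision where the trial has least of it. The lung-function hypotheses are tested in subgroups planned at 60 to 100 per group before withdrawal. The ABP, SNQ and PC20 have a single measurement after randomisation to set against Visit 3.

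**Working it through.** **Inputs from section VIII.B:** two-sided alpha 0.05; 15% withdrawal; SD of change in FEV1 0.375 L; 100, 80 or 60 per group, hence 85, 68 or 51 after withdrawal (n × 0.85). Allocation is 1:1 (section VI.A). The protocol gives neither rho nor a between-person SD of FEV1; both are assumptions below.

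**Step 1: reproduce the plan's table.** Power = Φ(d / (SD·√(2/n)) − 1.96). For n = 85 and d = 0.16 L: 0.375·√(2/85) = 0.0575; 0.16/0.0575 − 1.96 = 0.82; power 79.4%.

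| n per group (after withdrawal) | Effect, L | Stated power | Recomputed |
|---|---|---|---|
| 100 (85) | 0.16 / 0.17 / 0.19 | 80 / 85 / 90% | 79.4 / 84.0 / 91.0% |
| 80 (68) | 0.18 / 0.19 / 0.21 | 80 / 85 / 90% | 79.9 / 84.0 / 90.4% |
| 60 (51) | 0.21 / 0.23 / 0.24 | 80 / 85 / 90% | 80.7 / 87.2 / 89.8% |

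The noncentral t version puts all nine cells within 2 points of the stated power. The table is therefore correct for an unadjusted test of change.

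**Step 2: the variance ratio.** With equal variance σ² at Visit 3 and follow-up:
- change score: 2σ²(1 − rho)
- conditional on Visit 3: σ²(1 − rho²)
- ratio: (1 + rho)/2

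Generalised least squares on Visits 3 and 5 to 10, comparing a separate Visit 3 mean per arm with a common one, gives the same ratio for the Visit 3 to Visit 6 contrast: 0.90 at rho 0.80 and 0.957 at rho 0.913. For the taper-phase contrast (Visit 6 to Visit 10) the ratio is 0.953 to 1.0 over four correlation structures, a saving of 0 to 5%.

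**Step 3: what rho is plausible for FEV1.** From SD of change = σ√(2(1 − rho)), rho = 1 − 0.375²/(2σ²).
- σ = 0.6 L: 1 − 0.1406/0.72 = 0.80
- σ = 0.9 L: 1 − 0.1406/1.62 = 0.91
- rho = 0.5 would need σ = 0.375 L, and rho = 0.7 would need 0.48 L. These are small for adults of both sexes with no upper limit on FEV1.

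**Step 4: power with the SD replaced by 0.375·√((1 + rho)/2), at the 80% cells.**

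| rho | 85 per group, 0.16 L | 68 per group, 0.18 L | 51 per group, 0.21 L |
|---|---|---|---|
| change contrast | 79.4% | 79.9% | 80.7% |
| 0.9 | 81.4% | 81.9% | 82.7% |
| 0.8 | 83.4% | 83.9% | 84.6% |
| 0.7 | 85.5% | 85.9% | 86.6% |
| 0.5 | 89.5% | 89.8% | 90.4% |

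The gain is about 2 points at rho 0.9, 4 at 0.8, 6 at 0.7 and 10 at 0.5. At rho 0.8, 85 per group is worth 85/0.90, or about 94.

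**Step 5: does the RM-ANCOVA recover this?** That depends on its form, which is not stated. A time-constant covariate entered as a main effect shifts every visit equally and cancels from a within-person change. In 1,500 simulated trials with Visit 3 kept as a response and a covariate correlated 0.9 with it, the variance ratio was 1.000. With Visit 3 as a covariate for the later value it was 0.961 (theory 0.957).

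**The case against.** The strongest reply is that nothing here is wrong. Under randomisation the change contrast is unbiased with the correct type I error. Its standard error already allows for chance imbalance at Visit 3, and the power table uses the SD of change and matches the planned test. A reader might infer bias or overstated power; the documents support neither. All of this stands, and it limits the point to efficiency.

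A reader might also infer that the outcome's own baseline is ignored. It is not: it enters by subtraction, and FEV1 % predicted and log2 PC20 are on the covariate list.

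Nor is the adjusted model merely optional throughout. For secondary hypothesis 1 the section commits to an RM-ANCOVA within each subgroup adjusted for the appropriate baseline factors, and for hypothesis 2 it says that adjusted models will be evaluated. But these are additional to the RM-ANOVA that addresses each hypothesis, and step 5 shows that they may bring no gain.

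Finally, the protocol does not say that each arm has its own Visit 3 mean, and parameterisation is often left to the SAP. That reading is an inference. It is the ordinary meaning of a contrast of changes in an RM-ANOVA, and the power table is built on the same comparison. Because the protocol does fix change from Visit 3 as the lead test, the suggestion concerns a stated choice, not a missing detail.

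**Conclusion.** This is a free improvement in efficiency, not a correction of an error. It applies to FEV1, log2 PC20, ACT, ASUI, asthma-control and rescue-free days, ABP and SNQ, each of which has a value at Visit 3 and after randomisation.

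The direction is certain for any rho below 1; the size is conditional. For FEV1 the gain is about 2 to 4 power points, resting on an assumed between-person SD of 0.6 to 0.9 L. A gain near 10 points for FEV1 might be inferred from the general formula, but it fits poorly with the protocol's own SD of change. For the questionnaire scores, 6 to 10 points follows only if rho is 0.5 to 0.7 and the change contrast starts near 80% power. The protocol states neither.

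It would also be too broad to say that every secondary outcome is affected. Time to exacerbation, cold scores and ICS dose are not analysed as changes from Visit 3. The taper-phase contrast starts after randomisation and gains little.

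**What to change.** In section VIII.B, for the outcomes named above, make the lead repeated-measures model one of two forms:
- Visit 3 kept as a response, with a common mean across the arms; or
- post-randomisation visits only, with the participant's own Visit 3 value and its interaction with visit as covariates.

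Apply the same model within the BMI, race and corticosteroid-nonresponsive subgroups. Keep the unadjusted change contrast as a sensitivity analysis. Leave the power table as it is and describe it as conservative.

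The cost is one sentence and one changed model statement, with no new data, visits or participants. The common-mean form stays within the likelihood and missing-at-random framework of section VIII.C. The one drawback is that the reported effect will no longer equal the simple difference of the arms' mean changes, so show the raw mean changes alongside.

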 - (8) Vitamin D levels. Initial and post-randomization vitamin D levels will be compared to above asthma outcomes. The area under the curve (AUC) for vitamin D levels will be calculated for all individuals and compared to asthma control, quality of life and physiologic measures. In addition, an analysis will be performed restricted to those individuals who achieved sufficient vitamin D levels (>30 ng/ml) during the trial compared to those that did not.
 - (9) Corticosteroid responsiveness. Change in lung function in corticosteroid unresponsive and

- 1 responsive individuals will be evaluated. Corticosteroid-responsive airflow obstruction will be defined
- 2 as a ≥5% improvement in FEV₁ following systemic corticosteroids.
- 3 (10) Total inhaled corticosteroid dose. Cumulative inhaled corticosteroid received dose during all
- 4 study phases (phases I, IIa and IIb) will be calculated and compared to asthma control, quality of life
- 5 and physiologic measures.
- 6 (11) Colds. In all individuals experiencing a cold during the trial, the potential impact of vitamin D
- 7 on respiratory tract infections will be evaluated. The frequency and severity of colds, as reflected by
- 8 the peak Wisconsin Upper Respiratory Symptom Survey-21 (WURSS-21) score (86) during the cold,
- 9 will be compared between those in the vitamin D treatment group to those receiving placebo.
- Secondary analysis of the severity of the cold will evaluate the effect of the intervention on day 1 and
- 11 2 WURSS-21 scores.
- 12 (12) Airway inflammation. Response to vitamin D based on presence of airway inflammation (≥ 3%
- sputum eosinophils) at baseline (visit 3) and change over time in airway inflammation.
- 14 (13) Stress. Levels of perceived stress will be assessed using an adapted version of the Perceived
- 15 Stress Scale (PSS) (87) in all individuals.
- 16 (14) Sinonasal disease. Rhinitis and sinusitis symptoms will be assessed using a Sinonasal
- 17 Questionnaire (SNQ) (88) in all individuals.

IV. PROTOCOL OVERVIEW

A. Protocol design

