Pulmonary Function Testing. All participants will undergo spirometry at visits 1 and 3-10. Spirometric studies are performed in accordance with ATS recommendations (92) and AsthmaNet manuals of procedure (MOP). All participants will undergo methacholine bronchoprovocation at visits 3 and 6 [and visit 2 if no evidence of bronchodilator responsiveness at visit 1] in accordance with ATS recommendations (93) and AsthmaNet MOP. A positive response is considered a drop in the FEV₁ from post-diluent FEV₁ ≥20%.

Corticosteroid-responsiveness phenotype. Many patients with moderate to severe asthma (with bronchial hyperresponsiveness) do not demonstrate corticosteroid reversibility likely due to airway remodeling (6, 94). All participants will be characterized as corticosteroid responsive or nonresponsive based on reversibility of airflow obstruction at visit 4 following systemic corticosteroid provided at visit 3. Corticosteroid-responsive airflow obstruction will be defined as a ≥5% improvement in FEV₁ after the administration of 5 + 2 days of prednisone 40 mg/day measured at visit 4 compared to the baseline value at visit 3. If the participant's FEV₁ does not improve by at least 5%, they will be considered to have corticosteroid-nonresponsive airflow obstruction. We have chosen to define the corticosteroid responsive phenotype at visit 3 so that all participants will have completed 4 weeks of run-in medication (confirmed by adherence monitoring). Furthermore, we have used a cut-off of 5% change in FEV₁ based on our experience with systemic corticosteroid response (18). However, we will perform additional subset analysis using the median split, 7.5% and 10% change in FEV₁ as alternate

cutoffs [as they have been used to define inhaled corticosteroid response (17, 19)], as well as the proportion of participants who achieve normal lung function as defined by an FEV₁ ≥85% predicted.

Bronchodilator reversibility phenotype. Participants will undergo spirometry with bronchodilator reversibility testing and maximal bronchodilation as defined by the maximal achievable FEV₁ after levalbuterol (up to 360 mcg or 8 puffs). Participants will withhold medications as per the AsthmaNet MOP. Bronchodilator reversibility has been shown to predict subsequent inhaled corticosteroid response (17-19) and will be evaluated as a covariate potentially influencing the primary endpoint.

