Although the safe tolerable upper intake level for vitamin D was set at 2,000 IU/day in 1997 by the National Academy of Sciences Institute of Medicine for adults and children greater than 1 year of age, (119) recent analyses indicate that this level could safely be updated to 10,000 IU/d, well above our chosen daily dose of 4,000 IU/day (110, 120, 121). As a benchmark, this same (4,000 IU/d) dose has been employed by other investigators in studies in related diseases such as atopic dermatitis (e.g. by the NIAID-funded Atopic Dermatitis and Vaccinia Immunization Network) (122) and an ongoing maternal supplementation study (123).

VIII. POWER ANALYSIS AND STATISTICAL METHODOLOGY

A. Power Analysis

In order to have 90% power to detect a hazard ratio of 1.8 from a Cox regression model (a reduction in treatment failure rate from 40% in the control group to approximately 24-25% in the intervention group during the randomized treatment period), a sample size of 200 participants per group is required. This calculation assumes an overall alpha level of 0.05, a 2-sided test, and 15% withdrawal (Power Analysis and Sample Size (PASS) Software 2008).

B. Statistical analysis methods

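### The exploratory association between corticosteroid responsiveness and change in FEV1 from Visit 3 subtracts the same Visit 3 value on both sides and is biased upward

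*Protocol*

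**What the plan says.** Sections VI.D and VIII.B define corticosteroid responsiveness as the percentage improvement in FEV1 after the prednisone course, "measured at visit 4 compared to the baseline value at visit 3". The main cut-off is 5%. Alternatives are a median split, 7.5%, 10%, and FEV1 above 85% of predicted after the course.

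For the secondary outcomes, the repeated-measures models in VIII.B "evaluate the change over time from baseline (Visit 3" visit) to the close of the stable-dose phase at Visit 6, "as well as the change over time during the inhaled corticosteroid-taper phase".

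For the reduced-responsiveness hypothesis, VIII.B compares the arms within the less responsive participants. It then adds two exploratory analyses. The first estimates the treatment effect in responsive participants and tests the interaction. The second consists of "treating corticosteroid responsiveness as a continuous measure, and assessing its association with change in lung function in the repeated measures models". The second names no treatment interaction, no alternative baseline and no restriction to changes that omit Visit 3.

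Section III.D, item 9, lists "Change in lung function in corticosteroid unresponsive and" responsive participants as something to be evaluated. The protocol nowhere mentions that Visit 3 enters both quantities.

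**The concern.** The predictor contains minus Visit 3 FEV1 and also divides by it. The stable-phase outcome contains minus Visit 3 FEV1 too. Ordinary visit-to-visit variation at Visit 3 therefore pushes both in the same direction. This is mathematical coupling, with regression to the mean as its visible form.

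The trial's background rests on variable response to corticosteroids. A finding that participants who respond to prednisone go on to gain more FEV1 would be read as biology, although it can arise from noise in one spirometry session. Repeating the analysis with the 7.5%, 10% and median cut-offs would repeat the artefact and could look like confirmation. The cut-off at 85% of predicted uses Visit 4 alone and does not share this coupling.

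**Working it through.** **The plan's own figure.** VIII.B gives detectable arm differences of 0.16 to 0.21 L in the reduced-responsiveness subgroup, with 80 to 100 per group, "assuming an overall alpha=0.05, 2-sided tests, 15% withdrawal" and "standard deviation = 0.375 from the ACRN MIA trial". With δ = SD × √(2/n) × (z₀.₉₇₅ + z_power) and n reduced by 15%:
- 100 per group (85 evaluable), 80% power: 0.375 × √(2/85) × (1.960 + 0.842) = 0.161 L.
- 80 per group (68 evaluable), 90% power: 0.375 × √(2/68) × (1.960 + 1.282) = 0.209 L.

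The stated range reproduces and is not in dispute.

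**Algebra.** Write V3 = T + e3, V4 = T + R + e4, V6 = T + C + e6. T is true level, R true prednisone response (SD t), C true later change, and each e is visit-to-visit variation (SD s). If R and C are independent:
- cov(V4 − V3, V6 − V3) = var(e3) = s², which is positive.
- Spurious slope = s² / (2s² + t²).
- Spurious correlation r = s² / (0.375 × √(2s² + t²)), with the SD of change held at the plan's 0.375 L.

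**Sample size.** VIII.A states that "a sample size of 200 participants per group is required". So N = 400 × 0.85 = 340.

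**Size.** The protocol gives neither s nor t, so these values are assumptions. Rejection is approximated by Φ(r√338 − 1.96).

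| s (L) | t (L) | slope (L per L) | r | rejection at nominal 5% |
|---|---|---|---|---|
| 0.10 | 0.25 | 0.010/0.0825 = 0.12 | 0.093 | about 40% |
| 0.10 | 0.12 | 0.010/0.0344 = 0.29 | 0.144 | about 75% |
| 0.15 | 0.25 | 0.0225/0.1075 = 0.21 | 0.183 | about 92% |
| 0.15 | 0.12 | 0.0225/0.0594 = 0.38 | 0.246 | over 99% |

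Simulation over these values agrees: slopes 0.12 to 0.38 and rejection from just under 40% to nearly 100%. The false gap in change between responders and non-responders is 0.06 to 0.15 L.

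**Wider range.** A second null simulation used percentage responsiveness, 2000 runs per setting, N = 340 and SD of change 0.375 L. Assumed: mean FEV1 2.5 L, between-person SD 0.7 L, t of 0, 0.2 and 0.3 L, and 10% to 100% of the change variance due to visit-to-visit variation. Ranges are over t.

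| noise share of change variance | r, change from Visit 3 | rejection | rejection adjusted for Visit 3 | rejection, taper-phase change | rejection, treatment interaction |
|---|---|---|---|---|---|
| 100% (s = 0.265) | 0.38–0.48 | 100% | 100% | 4.8–5.1% | 6.6–9.4% |
| 50% (s = 0.188) | 0.23–0.34 | 99–100% | 98–100% | 4.5–5.4% | 5.9–6.7% |
| 25% (s = 0.133) | 0.13–0.24 | 68–99% | 62–99% | 4.4–5.3% | 5.0–5.9% |
| 10% (s = 0.084) | 0.06–0.15 | 19–78% | 17–77% | 5.2–6.1% | 5.2–5.4% |

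The arm difference within non-responders rejected 3.8 to 5.8% of the time.

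**Why adjusting for Visit 3 fails.** Given the observed Visit 3 value, a higher Visit 4 partly signals that the true level lies above what Visit 3 showed. Later FEV1 follows the true level, so the association persists.

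**Why taper-phase change is clean.** Visit 10 minus Visit 6 contains neither e3 nor e4.

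**Adjusting for Visit 1 instead.** Modelling later FEV1 on V4 − V3 in litres with Visit 1 as covariate rejected about 5 to 6% when any true shift between Visits 1 and 3 was unrelated to prednisone response. With an assumed run-in shift of SD 0.2 L correlated ±0.3 with prednisone response, it rejected between 21% and 65%, depending on settings.

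**The case against.** The strongest reply is that the sentence can be read as a continuous version of the treatment interaction. It sits under a hypothesis about the effect of vitamin D, the sentence before the two on exploratory analyses adds covariate-adjusted arm comparisons, the first exploratory analysis names the interaction test, and IX.A says the prednisone test serves to compare the vitamin D effect between responsive and non-responsive participants. On that reading there is essentially no problem. This shows that the intent may be sound. The words, however, describe the association of responsiveness with change and name no interaction.

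It can also be said that model terms for an exploratory analysis belong in the SAP. That would answer an omission, but the protocol itself fixes Visit 3 as the reference for both quantities.

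Three limits stand. Taper-phase change is not affected. Item 9 of III.D speaks only of evaluating change in the two groups and states no test between them, so the problem arises there only if such a comparison from Visit 3 is made. And the variability that sets the size is assumed.

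A reader might infer that the reduced-responsiveness hypothesis is itself biased. The documents do not support this: that hypothesis compares randomised arms within a subgroup defined before randomisation, and the coupling is equal in both arms.

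A reader might also set the false gap of 0.06 to 0.15 L against the 0.16 to 0.21 L in VIII.B. These are not like for like, because the latter are detectable differences between arms.

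**Conclusion.** The point holds for the marginal association between responsiveness and any change measured from Visit 3, and for any responder versus non-responder comparison of such change. The positive direction is certain from the protocol's definitions, provided FEV1 varies at all from visit to visit. A significant false result is not guaranteed. Over the assumed values the null rejection rate runs from about 19% to nearly 100%, always above 5%, and adjustment for Visit 3 leaves it at 17 to 100%.

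Taper-phase change and the arm contrasts keep their level. The treatment-by-responsiveness interaction stays between 5.0% and 6.9%, except for 9.4% at the extreme where all change is noise and prednisone response does not vary.

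No primary or secondary hypothesis test is biased and the analysis is labelled exploratory. Severity is minor to moderate.

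**What to change.** In VIII.B, state that the continuous responsiveness analysis, and every cut-off version of it, draws its inference from the treatment-by-responsiveness interaction. The interaction is already planned for the categorical definition; the change extends it to the continuous measure.

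If a marginal association is also reported, limit it to change during the taper phase, and say that the marginal association with change from Visit 3 will not be interpreted. Apply the same rule to item 9 of III.D. Do not rely on Visit 3 FEV1 as a covariate to solve the problem.

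A model of later FEV1 on Visit 4 minus Visit 3, adjusted for Visit 1 pre-bronchodilator FEV1, may serve only as a sensitivity analysis. It should carry the caveat that FEV1 may shift between Visits 1 and 3, because the run-in inhaled corticosteroid starts at Visit 2.

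The cost is protocol or SAP wording. No new data, visits or participants are needed.
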